3.1 Analysis Populations

Analysis populations or sets define the subjects to be included in an analysis. Analysis sets and their definitions are provided in this section. The analysis set will be identified and included as a subtitle of each table, figure, and listing. For each analysis set, the number and percentage of subjects eligible for inclusion will be summarized by treatment and cohort. A listing of reasons for exclusion from analysis sets will be provided by cohort and subject.

3.1.1 Randomized Set

Randomized Set includes all randomized subjects, classified according to the treatment to which they were randomized, regardless of the actual treatment received.

3.1.2 Full Analysis Set

The Full Analysis Set (FAS) includes all randomized subjects, classified according to the treatment to which they were randomized, regardless of the actual treatment received, who took at least 1 dose of study drug.

3.1.3 Safety Analysis Set

The Safety Analysis Set includes all randomized subjects, classified according to the actual treatment received regardless of randomized assignment, who took at least 1 dose of study drug. This is the main analysis set for all safety analyses.

3.1.4 PK-Related Sets

PK-related sets will be described in a separate PK analysis plan (PKAP).

3.2 Subject Grouping

For analyses based on the Randomized Set and FAS, subjects will be grouped according to the treatment to which they were randomized, regardless of actual treatment received. For analyses based on the Safety Analysis Set, subjects will be grouped according to the actual treatment

received, regardless of random assignment. The actual treatment received will differ from the randomized treatment only when the actual treatment differs from randomized treatment for the entire treatment duration.

3.3 Data Handling Conventions and Transformations

Subject age, collected at the Screening visit, will be used for analyses and will be presented in listings.

Total bilirubin values entered as < 0.2 mg/dL will be analyzed as 0.1 mg/dL; direct bilirubin values entered as < 0.1 mg/dL will be analyzed as 0.05 mg/dL (according to the methods of [Nehls and Akland, 1973](#)).

3.4 Missing Data and Outliers

3.4.1 Missing Data

In general, missing data will not be imputed unless methods for handling missing data are specified. Exceptions are presented in this document.

For missing last dose date of study drug, imputation rules are described in [Section 4.3.1](#). The handling of missing or incomplete dates for adverse event (AE) onset is described in [Section 5.1.5.2](#), and for prior and concomitant medications in [Section 5.3](#).

3.4.2 Outliers

Outliers will be identified during the data management review process. No sensitivity analyses will be conducted. All data will be included in the data analysis.

3.5 Analytic Definitions

3.5.1 Definition of Study Drug

The study drugs in this study are ABI-4334 and PBO.

3.5.2 Definition of Study Phase

3.5.2.1 All Cohorts Except Cohort A7

The following periods will be defined for all cohorts except cohort A7:

- On-Treatment Period: From first dose date/time through last dose date/time.
- Follow-Up Period: From last dose date/time +1 through end of study.

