1.4 Methods of Assigning Subjects to Treatment

1.4.1 Randomization

For cohorts A1-A4 and B1-B2, all subjects will be assigned a unique subject number at Screening and will be randomized to treatment with either ABI-4334 or placebo, upon meeting all protocol eligibility requirements. Randomization will be performed by an unblinded pharmacist. Subjects returning as part of cohort A6 will retain their original subject number and randomized treatment assignment.

Subjects in cohort A7 will take only ABI-4334. Subjects will be randomized, with 3 subjects being fed then fasted, and 3 subjects fasted then fed, in each of the two periods.

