3 GENERAL CONSIDERATIONS FOR DATA ANALYSES

Analysis results will be presented using descriptive statistics. For categorical variables, the number and percentage of subjects in each category will be presented; for continuous variables, the number of subjects (n), mean, standard deviation (SD) or standard error (SE), median, first quartile (Q1), third quartile (Q3), minimum, and maximum will be presented.

Summary tables will be presented by cohort and treatment. For cohort A7, summary tables will be presented fasting order (i.e. “fed,fasted” or “fasted,fed”).

No formal inference is planned in this study. Hence, no multiplicity adjustment is required.

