3.5.2.2 Cohort A7

The following periods will be defined for cohort A7:

- On-Treatment Period 1: Period 1 dose date
- Follow-Up Period 1: From Period 1 dose date +1 until Period 2 dose date.
- On-Treatment Period 2: Period 2 dose date.
- Follow-Up Period 2: From period 2 dose date +1 through end of study.

For each subject, end of study will be defined as completion of the last follow-up visit or premature study termination, or subject is lost-to-follow-up.

The study will end when the last subject completes the last visit of the follow-up period or is considered “lost to follow-up,” whichever is later.

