5.1.5 Treatment-Emergent Adverse Events

5.1.5.1 Definition of Treatment-Emergent Adverse Events

A treatment-emergent adverse event (TEAE) will be defined as any AE that has an onset date/time or worsening in severity from Baseline on or after the first dose date/time of study drug through end of study.

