5.1.6 Summaries of Adverse Events and Deaths

Treatment-emergent AEs will be summarized based on the Safety Analysis Set.

A brief, high-level summary of the number and percentage of subjects who experienced at least 1 TEAE in the categories described below will be provided by treatment and cohort. All deaths observed in the study will also be included in this summary. The number and percentage of subjects will be provided by SOC, PT, treatment, and cohort for each AE category and also by PT only in descending order of total frequency:

- TEAEs
- TEAEs by severity grade
- TEAEs related to study drug
- TE SAEs
- TE SAEs related to study drug
- TEAEs leading to study drug discontinuation
- TEAEs leading to study discontinuation
- TEAEs leading to death (ie, outcome of death)
- COVID-19 specific TEAEs
- COVID-19 specific TE SAEs

Multiple events will be counted only once per subject in each summary. Adverse events will be summarized and listed first in alphabetic order of SOC, and then by PT in descending order of total frequency within each SOC. For summary by severity grade, the most severe non-missing grade will be used for those AEs that occurred more than once in an individual subject during the study.

Data listings will be provided for the following:

- All AEs
- All treatment-related AEs
- All SAEs
- All treatment-related SAEs
- All AEs with severity of Grade 3 or higher
- All AEs leading to discontinuation of study drug
- All AEs leading to discontinuation of study
- All AEs leading to death (ie, outcome of death)
- All Deaths

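### The SAP applies subject-worded first-dose and end-of-study rules to returning Cohort A6 subjects, so their adverse events can fall in two cohort columns

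*Combined protocol and SAP*

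**What the plan says.** Cohort A6 is the fed food-effect cohort. Its subjects have completed one of the fasted cohorts A1-A5, wait at least 7 days and are dosed again. SAP 1.4.1 states: "Subjects returning as part of cohort A6 will retain their original subject number and randomized treatment assignment".

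SAP 3.5.2.1 covers every cohort except A7, and so includes A6. It sets one treatment period, "On-Treatment Period: From first dose date/time through last dose date/time", and one follow-up period, "Follow-Up Period: From last dose date/time +1 through end of study". SAP 3.5.2.2, 3.5.3.2 and 3.5.4 give A7, and only A7, separate periods, separate study days and a Period 2 Baseline. For all other cohorts, Baseline is the last value before the first dose.

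The rule that decides AE counts is SAP 5.1.5.1. An event is treatment-emergent if it starts or worsens "on or after the first dose date/time of study drug through end of study". End of study is worded by subject: "For each subject, end of study will be defined as completion of the last follow-up visit or premature study termination". That sentence stands in the A7 subsection, but protocol 4.5 says the same for the whole study.

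On layout, SAP 3 says "Summary tables will be presented by cohort and treatment", and SAP 5.1.6 says "Multiple events will be counted only once per subject in each summary". Neither says where a subject who belongs to two cohorts is shown.

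**The concern.** A returning subject has two doses, two scheduled Day 7 end-of-study visits and one subject number. The SAP recognised this problem for A7 and left A6 under rules built for a single course of dosing. Nothing states whether first dose, for A6, means the fasted or the fed dose, or which of the two end-of-study visits closes the source cohort's window.

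The proportion of subjects with AEs and abnormal laboratory results is the primary endpoint. An A1-A5 column normally has 6 active and 2 placebo subjects, so one subject placed in the wrong column moves it by 1/6 (16.7 percentage points) or 1/2 (50 points). Two programmers could build different primary safety tables from the same text.

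Laboratory data share the gap. SAP 5.2.1.1 grades treatment-emergent abnormalities against Baseline. New pre-dose evaluations are collected before the A6 dose, but SAP 3.5.4 gives them no explicit role.

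**Working it through.** **1. Subjects and columns.** The planned Part A number is reproduced: 5 fasted cohorts × 8 + 6 in A7 = 46, as in protocol 5.1. A6 adds no new subjects. With a full A6 column of 8 there are 40 + 8 + 6 = 54 cohort places for 46 people, so up to 8 people appear twice.

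**2. Exposure as a test of intent.** SAP 4.3.1 defines exposure as last dose date - first dose date + 1 and expects 1 day throughout Part A. With the fasted dose on Day 1 and at least 7 days of washout, the fed dose is on Day 8 or later.
- Subject-level dates: 8 - 1 + 1 = 8 days at least.
- Per-cohort dates: 1 - 1 + 1 = 1 day, which matches the SAP.

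**3. TEAE window test.** Assumed timeline: fasted dose Day 1, source-cohort Day 7 visit, fed dose Day 8, A6 Day 7 visit on Day 14. One AE starts on Day 2 (after the fasted dose) and one on Day 9 (after the fed dose). An event qualifies if first dose ≤ onset ≤ end of study.

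| First dose | End of study | Source window | A6 window | Fasted AE: source / A6 | Fed AE: source / A6 |
|---|---|---|---|---|---|
| Subject | Subject | 1-14 | 1-14 | yes / yes | yes / yes |
| Cohort | Subject | 1-14 | 8-14 | yes / no | yes / yes |
| Subject | Cohort | 1-7 | 1-14 | yes / yes | no / yes |
| Cohort | Cohort | 1-7 | 8-14 | yes / no | no / yes |

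Only the last row places each event in one column. The first row is the literal reading. The third is included for completeness.

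**4. Size.** Let p be the probability of at least one AE per dose. Assume it is equal and independent for the two doses, that all 6 active subjects return, and that they are shown in both columns. A column that captures both doses has expected proportion 1 - (1 - p)² instead of p.

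| p | 1 - (1 - p)² | Expected subjects of 6: one dose | Both doses |
|---|---|---|---|
| 0.1 | 0.19 | 0.60 | 1.14 |
| 0.3 | 0.51 | 1.80 | 3.06 |
| 0.5 | 0.75 | 3.00 | 4.50 |

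Under the literal reading this applies to both columns. With per-cohort first dose and subject-level end of study, it applies to the source column only. With both per cohort, the inflation is zero. As a concrete case of the literal reading, if one active subject has a fasted-only AE and another a fed-only AE, each column shows 2/6 (33.3%) instead of 1/6 (16.7%).

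**The case against.** A reader might infer that the SAP prescribes counting every returning subject's events twice. The documents do not support that. No section says that an event is to be shown in two cohort columns, and the once-per-subject rule in SAP 5.1.6 limits counting rather than multiplying it. Two-way overlap needs subject-level dates at both ends and the subject's events displayed in both columns.

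There is also evidence that a per-cohort reading was meant. The 1-day Part A exposure fits only that reading for A6. Protocol 4.2.1 lists A6 as a separate single-dose cohort, and Appendix 1b gives it its own Day 1 and Day 7 end-of-study visit. Subjects first complete the source cohort and are then enrolled into A6.

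This evidence carries weight but does not settle the matter. The 1-day figure also fails for A7, whose subjects receive two doses at least 7 days apart within one cohort, so it is not a reliable guide. The end-of-study label in Appendices 1a and 1b also covers the A7 periods, where the first such visit plainly does not end the subject's study. Protocol 4.4 says that food-effect subjects have a longer study duration, which fits a subject-level end of study.

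It is right that SAP 3.5.2.1 does not define TEAEs. Changing it alone would alter no AE count; SAP 5.1.5.1 and 3.5.4 govern the counts. It is also too strong to say that a fed/fasted tolerability difference would be hidden: by-subject listings of all AEs remain, no inference is planned, and the escalation reviews in protocol 10.6.1 use Day 1 to Day 4 data of the current SAD cohort rather than these final tables.

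**Conclusion.** The point holds as a defect in the stated rules, not as a demonstrated double count. SAP 5.1.5.1 and 3.5.4, together with 3.5.2.1, place A6 under subject-worded rules that span both doses when taken literally. Overlap is avoided only if both first dose and end of study are read per cohort. That reading is probably the intended one, but the SAP does not state it.

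The effect on the expected AE proportion ranges from none to 1 - (1 - p)² instead of p per affected column. The upper end rests on the assumptions in step 4 of the working. It falls with fewer returners, and disappears if A6 is not enrolled. Because the counts are themselves the primary safety result, the descriptive nature of the study does not remove the need to settle this before database lock.

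**What to change.** Amend SAP 3.5.2 to 3.5.4, 4.3.1, 5.1.5.1 and 5.2.1.1 as follows.

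- **Reference dates.** Define A6 first dose, study day, exposure and Baseline from the A6 dose, in the same way as A7 Period 2. A6 Baseline is the last non-missing value before the A6 dose. Align the Baseline wording repeated in SAP 5.2.3 and 5.3.
- **One column per event.** For AEs and laboratory abnormalities, the source-cohort window ends at that cohort's Day 7 end-of-study visit, as in the other fasted cohorts. The A6 window runs from the A6 dose to A6 end of study. SAP 5.1.5.1 has no A7 wording to borrow, so these windows must be written out.
- **Ongoing events.** An AE ongoing at the A6 dose counts in A6 only if it worsens from the A6 Baseline.
- **Gap events.** AEs starting between the source cohort's Day 7 visit and the A6 dose are listed separately. The washout has a minimum but no stated maximum, so extending the source window to the A6 dose would give returners longer observation than subjects in neighbouring cohorts.

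The cost is a few sentences of SAP text and a cohort-specific reference dose date in the analysis dataset. No new data are needed, because the A6 pre-dose evaluations are already scheduled in Appendix 1b.

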3.5.2.2 Cohort A7

The following periods will be defined for cohort A7:

- On-Treatment Period 1: Period 1 dose date
- Follow-Up Period 1: From Period 1 dose date +1 until Period 2 dose date.
- On-Treatment Period 2: Period 2 dose date.
- Follow-Up Period 2: From period 2 dose date +1 through end of study.

For each subject, end of study will be defined as completion of the last follow-up visit or premature study termination, or subject is lost-to-follow-up.

The study will end when the last subject completes the last visit of the follow-up period or is considered “lost to follow-up,” whichever is later.

3.5.3 Definition of Study Day

The first dose date of study drug will be calculated where applicable. The last dose date of study drug will be calculated where applicable. The last dose date of study drug will be the end date on study drug administration eCRF.

3.5.3.1 All Cohorts Except Cohort A7

Study Day 1 is defined as the first dose date of study drug. If the first dose date is missing, the date of randomization will be used.

For the On-Treatment Period, study days will be calculated from Study Day 1 and derived as follows:

- For days prior to the first dose: Assessment Date – Study Day 1.
- For postdose study days: Assessment Date – Study Day 1 + 1.

For the Follow-Up Period, the Follow-Up Study Day 1 will be defined as the day after the last dose date of study drug and the follow-up study day will be calculated from the last dose date and derived as Assessment Date – Last Dose Date of study drug.

3.5.3.2 Cohort A7

Period 1 Study Day 1 is defined as the period 1 dose date of study drug. Period 2 Study Day 1 is defined as the period 2 dose date of study drug.

Study days will be calculated for each study period.

In On-Treatment Period 1, for days prior to the first dose, Period 1 study days will be derived as Assessment Date – Period 1 Study Day 1.

For the Follow-Up Period 1, the Follow-Up Period 1 Study Day 1 will be defined as the day after the Period 1 study drug dose date and Follow-Up Period 1 study days will be calculated from Follow-Up Period 1 Study Day 1 and derived as Assessment Date – Follow-Up Period 1 Study Day 1 + 1. Follow-Up Period 2 will be treated similarly.

3.5.4 Definition of Baseline

For all analyses, Baseline will be defined as the last non-missing evaluation prior to the first dose date/time. For cohort A7, Period 2 Baseline will be defined as last non-missing evaluation prior to the dosing on Period 2 Study Day 1.

For all cohorts, except cohort A7 Period 2, Change from Baseline will be defined as the result at desired timepoint minus the result at Baseline. For cohort A7 Period 2, Change from Baseline will be defined as the result at desired timepoint minus the result at Period 2 Baseline.

3.5.5 Analysis Visit Windows

Analysis visit windowing will not be used for this study. Nominal scheduled study visits will be used as analysis visits. Unscheduled visits and premature termination visits that occur on or in place of a scheduled study visit will be mapped to the same analysis visit as the scheduled study visit.

3.5.6 Selection of Data in the Event of Multiple Records on Same Analysis Visit Day

Depending on the statistical analysis method, single values may be required for each analysis visit day. If a single value is needed, but multiple valid, nonmissing measurements exist in an analysis visit day, records will be chosen based on the following:

- For Baseline, the last nonmissing value on or prior to the first dose date of study drug will be selected, unless specified differently. If there are multiple records with the same time or no time recorded on the same day, the record with the lowest accession number will be used.
- For post-Baseline values, the latest record will be selected. If there is more than 1 record with sample collected on the same day with the same time, the retest record will be selected. If there is no clear indication for which record is the retest record, then the record with the lowest accession number will be used.

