8.3.3 Electrocardiograms

A standard 12-lead ECG will be obtained as indicated in [Appendix 1](#), [Appendix 2](#), and [Appendix 3](#). The ECGs will be measured in triplicates at 3 minutes apart only at Screening. Single ECGs will be collected thereafter, unless required by the Investigator.

Prior to the conduct of 12-lead ECGs, subjects should rest in a supine position for 10 minutes. Electrocardiograms should be conducted in accordance with local practice and equipment. The ECG assessment will include interpretation of the tracings (eg, rhythm, presence of arrhythmia or conduction defects, morphology, any evidence of myocardial infarction, or ST segment, T-wave, and Uwave abnormalities). The Investigator or a physician subinvestigator is responsible for reviewing and overreading the ECG interpretation, for assessing whether the ECG machine interpretation findings are accurate, appropriate, normal or abnormal, and for providing corrected interpretations as appropriate. In addition, any abnormal ECGs will be assessed for clinical significance.

Additional ECGs may be obtained if clinically indicated and will be obtained if abnormal and clinically significant or thought to be an error (eg, lead placement error, movement artifact, etc). Any additional relevant data obtained by the Investigator during the course of this study will be recorded in the subject's source documentation. The Investigator or a physician subinvestigator will review all ECGs, evaluate the results, and sign/date the tracing or report. For any ECG abnormality that the Investigator considers clinically significant, the Investigator will:

- Repeat the ECG
- Obtain follow-up ECG(s) if any significant abnormalities are detected after study drug administration to document resolution and as clinically indicated
- Record as an AE any ECG abnormality that: (1) is confirmed and the Investigator considers clinically significant; or (2) requires a subject to be discontinued from the study; or (3) the abnormality requires a subject to receive treatment

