9.10 Toxicity Management

Administration of study drug may be discontinued due to an adverse event. The Medical Monitor should be consulted prior to dose interruption or discontinuation of study drug, if possible, unless

the Investigator believes that immediate action is warranted to ensure the continued safety of subject, in which case the Medical Monitor should be notified immediately after.

Grade 3 and 4 clinically significant laboratory abnormalities (reported as AEs) should be confirmed by repeat testing within 3 days of receipt of results and before study drug discontinuation, unless such a delay is not consistent with good medical practice.

Any questions regarding toxicity management should be directed to the Medical Monitor.

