5.2.3 Summaries of Numeric Laboratory Results

Descriptive statistics will be provided by treatment and cohort for each laboratory test specified in the study protocol as follows:

- Baseline values
- Values at each post-Baseline visit
- Change from Baseline at each post-Baseline visit

A Baseline laboratory value will be defined as the last measurement obtained on or prior to the date/time of first dose of study drug. Change from Baseline to a post-Baseline visit will be calculated for any post-Baseline visit including follow-up visits. For Cohort A7 Period 2, Period 2 Baseline and Change from Period 2 Baseline will be used instead.

In the case of multiple values in a visit day, data will be selected for analysis as described in [Section 3.5.6](#).

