5.5 Electrocardiogram Results

A shift table of the Investigators' assessment of electrocardiogram (ECG) results at each visit compared with Baseline values will be presented by treatment and cohort using the following categories:

- normal
- abnormal (not clinically significant)
- abnormal (clinically significant)
- missing/not done

The number and percentage of subjects in each cross-classification group of the shift table will be presented. Subjects with a missing value at Baseline or post-Baseline will not be included in the denominator for percentage calculation.

A by-subject listing for ECG assessment results will be provided by cohort, subject number, and visit in chronological order.

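### A normal same-day repeat replaces the clinically significant ECG that prompted it in the by-visit shift table, the only ECG summary the SAP plans

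*Combined protocol and SAP*

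**What the plan says.** **Mapping.** SAP 3.5.5 uses nominal visits without windows, and adds: "Unscheduled visits and premature termination visits that occur on or in place of a scheduled study visit will be mapped to the same analysis visit".

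**Selection.** SAP 3.5.6 applies "If a single value is needed, but multiple valid, nonmissing measurements exist in an analysis visit day". Its post-Baseline rule is: "For post-Baseline values, the latest record will be selected". If two records carry the same time, the retest is preferred.

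**ECG table.** SAP 5.5: "A shift table of the Investigators' assessment of electrocardiogram (ECG) results at each visit compared with Baseline values will be presented". The categories are normal, abnormal without clinical significance, abnormal with clinical significance, and missing. A by-subject listing accompanies the table. The section plans no other ECG summary and states no rule for several tracings at one visit.

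**ECG repeats.** Protocol 8.3.3: "For any ECG abnormality that the Investigator considers clinically significant, the Investigator will" repeat it, among other steps. No time limit is given. The same section calls for an adverse event record if the abnormality is confirmed and clinically significant, leads to discontinuation from the study, or needs treatment.

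**Laboratory.** SAP 5.2.3 adopts the selection rule by cross-reference: "In the case of multiple values in a visit day, data will be selected for analysis as described in" Section 3.5.6. Protocol 9.10 says that clinically significant Grade 3 and 4 laboratory abnormalities "should be confirmed by repeat testing within 3 days of receipt of results and before study drug discontinuation".

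**The concern.** A latest-record rule is harmless when extra records arise for reasons unrelated to the result. Here they do not: the protocol orders an ECG repeat because the tracing was judged clinically significant. The records open to displacement are therefore selectively the abnormal ones, and what displaces them may be a normal repeat.

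At stake is the description of transient ECG findings in a first-in-human study. If such a finding leaves the only ECG table and does not qualify as an adverse event, a reader of the summary tables will not know that it occurred.

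**Working it through.** The documents give no figure to reproduce, so the check applies the two SAP rules to illustrative records. Each record goes to the visit day on which it falls, and the latest is kept.

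**Where the ECG mechanism operates.** It is clearest on days with one planned post-dose ECG:
- Part A (Appendices 1a and 1b): Days 2, 4 and 7.
- Part B (Appendix 2): 3 and 7 days after the last day of dosing.

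Subjects are in the clinic until discharge on Day 4 in Part A and Day 11 in Part B, so a same-day repeat is feasible on the earlier of these days.

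**Cases.**

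| Records | By-visit table | Other summaries |
|---|---|---|
| ECG clinically significant on Day 4, normal repeat later on Day 4 | Day 4 normal: finding displaced | No other ECG table; listing only, unless an adverse event |
| ECG clinically significant on Day 4, repeat on Day 5 | Day 4 stays clinically significant | Not needed |
| Laboratory Grade 3 on Day 3, Grade 0 repeat later on Day 3 | Day 3 value displaced | Maximum-grade table still shows Grade 3 |
| Laboratory Grade 3 on Day 3, repeat on Day 4 or 5 | Day 3 value stays; a Day 5 repeat competes with the scheduled Day 5 sample | Maximum-grade table shows Grade 3 |

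**Do adverse events catch the first case?** Take the three conditions in Protocol 8.3.3 in turn. The repeat is normal, so the finding is not confirmed. Suppose that it needs no treatment and causes no discontinuation. None of the conditions is then met. Protocol 9.7 adds abnormal assessments with signs or symptoms, if they meet the adverse event definition. An asymptomatic, unconfirmed, untreated finding therefore need not reach the adverse event tables.

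**Size for one subject.** Cohorts A1-A5 and B1-B2 allocate 6 to active drug and 2 to placebo.
- Active arm: 1/6 = 16.7% becomes 0/6 = 0%.
- Placebo arm: 1/2 = 50% becomes 0/2 = 0%.

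A displaced finding is not a missing one, so the subject stays in the denominator. Nothing in the documents allows the frequency of such findings to be estimated.

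**Laboratory.** SAP 5.2.1.1 counts a treatment-emergent abnormality at any post-Baseline time point, 5.2.1.2 takes the most severe grade, and 5.2.2 takes the highest direct bilirubin. None of these depends on the selection rule. What remains exposed is the by-visit value and change-from-Baseline table. For tests in Protocol Table 2 that have no grade in Appendix 4 (for example GGT, LDH, blood urea nitrogen, chloride and reticulocytes), that is the only planned summary table, although the listings flag out-of-range values.

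**The case against.** **SAP 5.5 does not refer to 3.5.6**, whereas 5.2.3 and 5.3 do. This is true, and the application to ECG is an inference. But the shift table needs one category per subject per visit, and 3.5.6 is the only rule offered for choosing one. If it does not apply, the table has no rule at all, and that also needs correcting.

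**The repeat may fall on another day.** Protocol 8.3.3 sets no time, and a later-day repeat leaves the prompting tracing in place. This stands. The mechanism is conditional on a same-day repeat.

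**Other records keep the finding.** The listing retains every tracing, and the Data Review Committee is unblinded. Confirmed or treated findings enter the adverse event tables. This stands too, and it limits the problem to unconfirmed, untreated findings in the summary tables.

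**Laboratory results.** A reader might infer that mean laboratory changes are attenuated by some material percentage. Such a figure can be produced by supposing that every value beyond a set number of standard deviations is repeated the same day. The documents describe no such policy. The stated trigger is a clinically significant Grade 3 or 4 abnormality reported as an adverse event, with repeat testing within 3 days of receiving the result. Protocol 8.3.5 admits only central-laboratory results to the analysis, so displacement would need a result returned and a second central sample drawn on one visit day. Turnaround is not stated, but nothing suggests that this would be common.

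**Conclusion.** The point holds for the ECG shift table. As written, the SAP lets a normal same-day repeat remove a clinically significant finding from the only ECG summary it plans. In a cohort's active arm, one such subject is the difference between 16.7% and 0% at that visit. This rests on three conditions: 3.5.6 governs the ECG table, the repeat is on the same visit day, and the finding does not otherwise qualify as an adverse event. The frequency is unknown.

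For laboratory data the same rule can alter by-visit values and changes from Baseline, but only through same-day repeats, and no percentage loss can be supported.

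A reader might also infer that the tables serving the primary objective are biased towards no effect. The documents do not support that. The primary endpoint (Protocol 3.2.1) names adverse events, discontinuations due to them, and abnormal laboratory results. The graded laboratory tables keep the worst value, and ECG is not a named component.

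**What to change.** 1. In SAP 3.5.5 and 3.5.6, state that by-visit summaries use the scheduled record. Use an unscheduled or repeat record only if the scheduled one is missing or documented as technically invalid. The protocol already gives examples of technical failure: lead misplacement or movement artifact in 8.3.3, and a hemolyzed sample in 5.4.
2. Cross-refer to this rule from SAP 5.5. Say there whether a visit means the day or the time point where several ECGs are planned on one day; otherwise the scheduled record is not unique.
3. Add one shift table from Baseline to the worst post-Baseline Investigator ECG category over all valid tracings, including unscheduled ones, by treatment and cohort.

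Worst values belong in that separate table and not in the by-visit one, because a worst-of-several category set against a single last-value Baseline rises with the number of tracings. The new table has the same property and should be read against placebo.

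The cost is SAP wording and minor programming before database lock. No new data are needed.
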